## Subgroup analyses

To explore whether the intervention's effects vary among different demographic or clinical subgroups, the primary analysis will be repeated within the following subgroups:

- a. Children without neurodevelopmental disorders (ASD, ADHD) compared with children with neurodevelopmental disorders at baseline and at end-of-intervention (1.5 years follow-up).
- b. Families with young children, i.e., 6-9 years at baseline compared with families with older children, i.e., 10-12 years at baseline.
- c. Families with low functioning at baseline (characterized by the 35% lowest combined scores in CGAS, HOME and PSP).
- d. Families where all family members (parents and all children) have been participating in at least the introductory sessions of VIA Family compared with families where not all family members participated.
- e. Families whose primary motivation to participate at baseline was to receive support compared with families whose primary motivation was to support a scientific project.

Estimated treatment differences from the subgroups will be reported in forest plots.

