and sex (registered at birth) as fixed effects and a random effect of family to address non-independence among siblings within the same family.

Changes in parent- and family-specific outcomes (FAD, PSP, PSS) including allocation group, baseline measurement, and parental diagnosis as covariates.

Mean differences in change between the VIA Family intervention and TAU groups, along with a 95% confidence interval, will be reported with corresponding p-values.

Model assumptions will be assessed using residual diagnostics. Severely skewed outcomes will be log-transformed prior to analysis.

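### The subgroup section asks whether the effect varies, but plans only separate within-stratum estimates and no between-stratum contrast; two of its stratum definitions are post-randomisation

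*SAP*

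**What the plan says.** The SAP's Subgroup analyses section states its aim as exploring whether "effects vary among different demographic or clinical subgroups". The method is one clause: "the primary analysis will be repeated within the following subgroups". The output is one sentence: "Estimated treatment differences from the subgroups will be reported in forest plots".

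Five items follow. Items a, b, d and e each name two groups to be compared. Item c names one.

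- **a** separates children without ASD or ADHD, "compared with children with neurodevelopmental disorders at baseline and at end-of-intervention (1.5 years follow-up").
- **b** reads "Families with young children, i.e., 6-9 years at baseline compared with families with older children" (10-12 years).
- **c** reads "Families with low functioning at baseline (characterized by the 35% lowest combined scores in CGAS, HOME and PSP").
- **d** separates families by whether every member was "participating in at least the introductory sessions of VIA Family".
- **e** separates families by their main motive for joining, recorded at baseline.

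The model to be repeated is given under Primary and secondary analyses. For SDQ it has fixed effects for allocation, baseline measurement, child age and sex, and a "random effect of family to address non-independence among siblings within the same family". It has no allocation-by-subgroup term.

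**The concern.** Whether an effect varies is a question about the difference between two treatment effects. The plan produces the two effects and stops. No difference, interval or test is specified, so the reader of the forest plot has to judge variation by eye, and the section gives no rule for doing so.

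A second problem is separate from the first. Attendance at VIA Family sessions happens after allocation and has no stated meaning in the TAU arm. Diagnosis at the end of the intervention may itself be affected by allocation. A VIA Family versus TAU difference within strata formed in these ways is not protected by randomisation, and for d the SAP does not say which TAU families belong in which row.

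At stake is an honest exploratory estimate with its uncertainty. No decision hangs on it.

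**Working it through.** **1. Does any part of the plan yield the contrast?** The Subgroup analyses section gives refitting within strata and a plot. The primary model has no interaction term. The reporting rule under Primary and secondary analyses covers the difference between arms, not a difference between strata. Following the SAP to the letter therefore never gives the between-stratum contrast.

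**2. Which items are fixed at baseline?** Items b, c and e are, and so is the baseline part of a. Item d and the end-of-intervention part of a are not. The wording of a can mean one joint condition or two analyses; either way it uses post-baseline status.

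**3. Are the baseline items fully defined?** Background and Aim allows more than one eligible child per family, and the model includes siblings. A family with a 7-year-old and an 11-year-old therefore fits both strata of b, and no rule assigns it. Item c gives no way of combining three measures. CGAS is scored per child, PSP appears for two parents in Table 2, and HOME can be done in two homes (Table 1, footnote 2).

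**4. Precision of the contrast.** The SAP gives no sample size, SD or power, so there is no figure of its own to reproduce. Assume independent strata holding shares f and 1-f of the information:

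SE(interaction) / SE(overall) = sqrt(1/f + 1/(1-f))

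- f = 0.50: sqrt(2 + 2) = 2.00
- f = 0.35 (the cut in c): sqrt(2.857 + 1.538) = 2.10

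At an assumed overall power of 80%, the overall noncentrality is 1.960 + 0.842 = 2.802. For a between-stratum difference equal to the overall effect, the interaction noncentrality is 2.802/2.00 = 1.40 or 2.802/2.10 = 1.34. Two-sided power at 5% is then about 29% or 27%.

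**5. What reading rows by significance would do.** Let the true effect be the same in both strata. With overall noncentrality n = 1.96 + z(power), or 0 under no effect, a stratum with share f reaches p < 0.05 with probability h = P(|Z + n·sqrt(f)| > 1.96). The chance that exactly one stratum does so is h1(1-h2) + h2(1-h1).

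| Assumed overall power | 50/50 split | 35/65 split |
|---|---|---|
| no effect | 9.5% | 9.5% |
| 20% | 22% | 22% |
| 50% | 41% | 42% |
| 80% | 50% | 53% |
| 90% | 47% | 51% |
| 99% | 24% | 31% |

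Worked case at 80% power, 35/65: h1 = 0.381 and h2 = 0.617, so 0.381 × 0.383 + 0.617 × 0.619 = 0.53. An interaction test would give 5% per factor throughout.

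**6. Could a reader rebuild the contrast from the plot?** For strata made of whole families, approximately, if the rows carry intervals. Where siblings can fall in different strata (a, and b if read per child), separate fits cannot carry their covariance. If a share s of children has a sibling in the other stratum, with intraclass correlation ICC, the rebuilt SE is too large by 1/sqrt(1 - s·ICC). For assumed s of 0.1 to 0.4 and ICC of 0.2 to 0.5, that runs from 1/sqrt(0.98) = 1.01 to 1/sqrt(0.80) = 1.12. The error is small and conservative.

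**The case against.** The strongest reply is that the SAP plans to display estimates, not to classify strata by significance. That is right. A reader might infer from the table in the working that the plan will produce false subgroup claims about half the time. The document does not support this. It adopts no such reading, it states no power, and the rate falls on both sides of the 50-90% range. The figures describe a misreading that the plan leaves open.

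It is also fair that the interaction test would itself miss about 71-73% of differences as large as the whole treatment effect at 80% overall power. The gain is an honest interval, not better detection. The sibling covariance changes little, by step 6.

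A reader might also infer that c has no comparison group and cannot be run. The remaining families are the natural complement, so this needs a few words only. The gap in b affects only families with children in both age bands, and the SAP does not say how many there are. How to combine the measures in c, and whether b works by child or by family, are choices for the trial team; no passage makes one of them correct.

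None of this supplies the missing contrast, and none of it restores randomisation to d or to the post-baseline part of a.

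**Conclusion.** The point stands in limited form. The section's stated question is not answered by its stated method, because the between-stratum difference and its interval are never estimated. Item d and the end-of-intervention part of a should not be presented as subgroup treatment effects. The first statement rests on the text alone; the second rests on the text and the general principle that strata formed after allocation lose the protection of randomisation. Neither depends on assumed power.

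The numerical results are illustrations: a normal approximation, independent strata, and overall power assumed because the SAP gives none. The section is exploratory and the primary SDQ comparison is untouched, so this is a change the plan should make, not a threat to the trial's main conclusion.

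**What to change.** For each baseline-defined factor (a at baseline, b, c against the remaining families, e), fit the primary SDQ mixed model once on the full ITT set. Add the subgroup main effect and the allocation-by-subgroup interaction, and keep the family random effect. Report the interaction estimate with its 95% CI, labelled exploratory, and take the forest-plot rows from that same model.

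Report d and the end-of-intervention part of a descriptively only. An interaction term does not repair strata formed after randomisation.

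Before analysis, write down one rule for families with children in both age bands (for example each child's own age, or the youngest child) and one rule for combining CGAS, HOME and PSP in c (for example a mean of standardised baseline scores). These are examples; what matters is that one is fixed in advance.

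The cost is SAP wording and two model terms per two-level factor. The interaction intervals will be wide, so the SAP should add that a non-significant interaction is not evidence that the effect is constant.

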## Hypotheses

We expect that the experimental intervention VIA Family has positively impacted long term improvements in parenting, home environment, parent- and family functioning and other parental and family-related factors of protection for their children. We therefore expect that we will observe greater improvements in child functioning (CGAS), less signs of mental health (SDQ), improved child quality of life (KIDSCREEN) and improved self-esteem (TIM) at 4-years follow-up, along improvements in parent and family related outcomes (PS, PSS, HOME, FAD, PSP) in families allocated to VIA Family compared with TAU.

The primary hypothesis is:

- The VIA Family intervention will demonstrate a superior change in SDQ from baseline (timepoint 0) to 4-year follow-up (timepoint 2) compared with TAU.

The secondary hypotheses are:

- The VIA Family intervention will demonstrate superior change in CGAS, KIDSSCREEN, TIM, HOME, FAD, PSS, PS, and PSP, respectively from baseline (timepoint 0) to 4-year follow-up (timepoint 2) compared with TAU.

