### Handling of missing data

Characteristics of dropouts and completers will be compared between the allocation groups in descriptive tables to identify any possible systematic patterns or reasons for participant discontinuation. Reasons for dropout will be reported.

Missing data in the primary and secondary analyses will be handled by standard multiple imputations using the mice-package and Amelia-package in R. Missing values in each treatment arm separately will be imputed 100-fold including the variables specified in Table 2 below. Convergence will be assessed by traceplots.

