**Table 2: Variables for imputation on missing data.**

*Unless specified otherwise, data from baseline, 18 months follow-up, and 50 months follow-up will be included.*

Child	Parent/family	Teacher
Covariates	Covariates	
Age a	Age a	
Sex at birth a	Parental SMI diagnosis a	
Out-of-home placement b,c	Parents living together	
Clinician-rated interview	Clinician rated interview	Surveys about the child
CGAS score	PSP, Index parent, total score	TRF, total score a,b
KSADS, any diagnoses (binary: yes/no) a,b	PSP, other parent, total score	BRIEF, total score a,b
	HOME , total score	SRS, total score a
Cognitive tests	Surveys about the child	
RIST – total score a	CBCL, total score a,b	
TOMAL-II total score a	BRIEF, total score a,b	
Coding (WISC) total score a	SRS, total score a	
RCFT - total score a	SDQ, total score	
Self-report questionnaires	Self-report questionnaires	
This Is Me, total score	PSS Index, total score	
KIDSCREEN, total score	PSS, other parent, total score	
a Baseline data		

b 18 months follow up data (end-of-intervention)			
c 50 months follow up data			

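### Table 2 leaves motivation (subgroup e) and ASD/ADHD status (subgroup a) out of the imputation model, so any true difference in effect between those strata would be attenuated in the forest plots

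*SAP*

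**What the plan says.** The primary hypothesis concerns SDQ: "The VIA Family intervention will demonstrate a superior change in SDQ from baseline (timepoint 0) to 4-year follow-up (timepoint 2) compared with TAU" (SAP, Hypotheses).

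On missing data the SAP states: "Missing data in the primary and secondary analyses will be handled by standard multiple imputations using the mice-package" together with a second R package, and "Missing values in each treatment arm separately will be imputed 100-fold including the variables specified in Table 2 below" (SAP, Handling of missing data). Table 2 lists "SDQ, total score" without a footnote, so SDQ enters at baseline, 18 months and 50 months. For child diagnosis it lists only "KSADS, any diagnoses (binary: yes/no"), at baseline and 18 months.

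Under Subgroup analyses, "the primary analysis will be repeated within the following subgroups", and the treatment differences go into forest plots. Item a is "Children without neurodevelopmental disorders (ASD, ADHD) compared with children with neurodevelopmental disorders at baseline and at end-of-intervention (1.5 years follow-up"). Item e contrasts "Families whose primary motivation to participate at baseline was to receive support" with families who mainly wished to support research.

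The SAP does not say that imputation is redone within subgroups, or that variables defining subgroups are added to the imputation model.

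**The concern.** Imputing each arm separately lets the treatment effect vary with a covariate only if that covariate, or something that carries its information, is in the imputation model. If the stratum variable is absent, a child with missing 4-year SDQ receives a value drawn from a regression fitted to the whole arm. In the VIA Family arm, children in a stratum that gains nothing are then imputed with part of the benefit seen in the other stratum, and the reverse.

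The section exists to explore whether the effect varies. If it does, both rows of the forest plot move towards the overall effect, and the pattern looks more consistent than it is. A reader of the plot could not detect this.

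**Working it through.** **Step 1. Which subgroup variables are in Table 2?**

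| Item | Defining variable | In Table 2? |
|---|---|---|
| a | ASD/ADHD status, baseline and 18 months | No. Partial proxies: any K-SADS diagnosis and BRIEF (baseline, 18 months), SRS (baseline) |
| b | Child age | Yes |
| c | CGAS, HOME, PSP | Yes |
| e | Baseline motivation | No, and no evident proxy |

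**Step 2. Size of the dilution without a proxy.** The SAP gives no missing rate, SD, sample size or effect size, so there is no figure of its own to reproduce and everything below is assumed. Let m be the fraction of 4-year SDQ missing (at random, equal across arms and strata), e0 and e1 the true stratum effects, and p the share of children in stratum 1. If nothing in the imputation model carries the stratum:

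- average effect: ē = (1 − p)·e0 + p·e1
- estimated effect in stratum s: (1 − m)·e_s + m·ē
- estimated contrast: (1 − m)·(e1 − e0)

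The fraction of the contrast lost is therefore m.

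Take e0 = −0.50, e1 = 0 (roughly SD units), p = 0.30 and m = 0.30:

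- ē = 0.70 × (−0.50) + 0.30 × 0 = −0.35
- stratum 0: 0.70 × (−0.50) + 0.30 × (−0.35) = −0.455
- stratum 1: 0.70 × 0 + 0.30 × (−0.35) = −0.105
- contrast: −0.105 − (−0.455) = 0.35, against a true 0.50
- overall: 0.70 × (−0.455) + 0.30 × (−0.105) = −0.35, unchanged

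The last line shows why this mechanism leaves the overall result alone.

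**Step 3. Simulation.** Same effects and p; 20,000 children, 6 replicates, 5 imputations by Bayesian linear regression within arm, random dropout, 18-month SDQ always observed, then a baseline-adjusted regression within each stratum. True contrast 0.50.

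| Missing | No proxy, no effect yet in 18-month SDQ | Proxy r = 0.5 | Proxy r = 0.7 | Stratum variable added (no proxy) |
|---|---|---|---|---|
| 10% | 0.460 | 0.465–0.492 | 0.466–0.477 | 0.502 |
| 20% | 0.412 | 0.423–0.462 | 0.451–0.474 | 0.505 |
| 30% | 0.364 | 0.384–0.441 | 0.424–0.485 | 0.506 |
| 40% | 0.311 | 0.359–0.418 | 0.386–0.459 | 0.506 |

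The proxy ranges run over 0, 50 or 100% of the effect being already present in 18-month SDQ. With no proxy but the full effect present at 18 months, the contrast at 30% missing is 0.449, a loss of (0.50 − 0.449)/0.50 = 10%. Every run without the stratum variable fell below 0.50.

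**Step 4. When 18-month SDQ is also missing.** A second simulation used 600,000 per arm, two equal strata, SDQ SD 6, effects of −3 and 0 points, and half of the 4-year effect passing through 18-month SDQ. With 30% missing at 4 years:

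- If half of those children also lack 18-month SDQ, the contrast falls from 3.00 to 2.34, a loss of 0.66/3.00 = 22%.
- If all 18-month scores are seen, the loss is 13%.

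With 40% missing and no 18-month scores among the dropouts, the contrast is 1.77, a loss of 1.23/3.00 = 41%, in line with the 40% from Step 2. With the stratum variable included, the contrast was 2.98 to 3.04.

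**The case against.** **The SAP does not fix how subgroup rows are imputed.** Its missing-data section names the primary and secondary analyses only, and repeating an analysis within a subgroup could include imputing within it. The problem would then vanish. This stands as an ambiguity. However, stratification by arm is the only one stated and Table 2 is the only variable list given, so reusing one set of imputations is the natural reading.

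**The bias is conditional.** A reader might infer that the rows for items a and e are biased whatever the truth. The documents do not support that: with no true difference in effect there is nothing to dilute. The error also runs towards sameness, so it does not create a false subgroup claim.

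**The size is assumed.** A reader might take the 22% loss as an estimate for this trial. It is not, because the SAP supplies none of the inputs. The bias may also be small beside the noise. Assume SD 6, baseline correlation 0.65 and n children per arm per stratum. The residual SD is 6 × √(1 − 0.65²) = 4.56 and the SE of the contrast is 4.56 × √(4/n): 1.8, 1.3 and 0.9 for n = 25, 50 and 100. A bias of 0.66 is then about 0.4 to 0.7 of one SE, before clustering and missing data widen it. This argues for modest weight, not for leaving the omission in place.

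**Item a has proxies.** This stands. At 30% missing and r = 0.7 the loss is (0.50 − 0.485)/0.50 = 3% to (0.50 − 0.424)/0.50 = 15%. Item e has no such help and is the stronger case.

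**Adding the variable may not remove all bias.** The simulations assumed a fully observed stratum, a common baseline slope and random dropout. If slopes differ by stratum and dropout depends on baseline, a main effect alone does not guarantee unbiased strata.

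**Conclusion.** The point holds in a limited form. Table 2 omits the variables that define subgroups a and e, and if one set of arm-wise imputations is reused, a true difference in effect between those strata is attenuated. Under random dropout the loss is at most roughly the fraction of 4-year SDQ that is missing: about 8% of the contrast at 10% missing (0.460 of 0.50) and about 38% at 40% (0.311 of 0.50). It is smaller for item a and wherever 18-month SDQ is observed.

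It would go too far to infer that the primary or secondary results are compromised. The mechanism redistributes effect between strata and leaves the average alone. The analyses concerned are exploratory, so this is a cheap improvement and not a flaw in the trial's main conclusions. The variable for item d is also absent from Table 2, but TAU families have no VIA Family sessions to attend. That is a separate problem, which this change would not solve.

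**What to change.** Add to the Table 2 imputation model, in both arms:

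- baseline motivation category;
- ASD/ADHD status (yes/no) at baseline and at 18 months, since item a refers to both times.

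Keep the any-diagnosis variable. Replacing it with the ASD/ADHD indicator would save a column but take a predictor away from the imputation behind the primary analysis.

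Add one sentence to Subgroup analyses stating that items a and e are run on these imputations. Because the arms are imputed separately, a main effect of the stratum in each arm's model already allows the treatment effect to differ between strata.

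The cost is a few more binary columns in the imputation model, with 18-month status itself imputed where it is missing, and one sentence in the SAP.

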### Statistical Analyses

All analyses will be performed in the intention-to-treat (ITT) population including study participants as randomized regardless of treatment adherence and dropout status. The analyses will be conducted using the statistical software R^11 after the last participant completes the follow-up assessment and after the formulation of the statistical analysis plan. A two-tailed p-value of < 5% will be considered statistically significant.

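### Subgroup item a forms strata partly from ASD/ADHD status at 18 months, after allocated treatment, so its within-stratum arm differences are not protected by randomisation

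*SAP*

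**What the plan says.** The SAP's Subgroup analyses section gives its purpose as "To explore whether the intervention's effects vary among different demographic or clinical subgroups". The method is that "the primary analysis will be repeated within the following subgroups", and "Estimated treatment differences from the subgroups will be reported in forest plots". The primary analysis concerns "superior change in SDQ from baseline (timepoint 0) to 4-year follow-up (timepoint 2) compared with TAU".

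Item a compares children who have neither ASD nor ADHD "with children with neurodevelopmental disorders at baseline and at end-of-intervention (1.5 years follow-up"). A footnote to Table 2 identifies the 18-month visit as the end of the intervention, so the second time point in item a falls after the full course of allocated treatment.

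Items b (child age), c (low functioning) and e (motivation to take part) are each tied to baseline. Item d concerns session attendance and is a different matter. Item a is the only clinical characteristic in the list that is read at a later visit.

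**The concern.** A subgroup analysis of effect modification asks whether the effect differs between kinds of children. The characteristic therefore has to be fixed before allocation can influence it. Within a stratum defined at baseline, VIA Family and TAU children are still randomised groups. Within a stratum defined at 18 months they are so only if allocation has no bearing on who carries the diagnosis.

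The SAP gives reason to doubt that. Its Hypotheses section expects VIA Family to improve child functioning and SDQ-rated mental health, and a treatment that changes symptoms can change whether a child meets symptom-based criteria. Footnote 1 of Table 1 defines a current diagnosis by a window of 8 weeks, so diagnostic status as recorded there can change between visits.

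If one arm has more diagnoses at 18 months, borderline children in that arm move from the without-diagnosis to the with-diagnosis stratum. The first stratum loses its most affected children and the second gains its least affected. Both then look better in that arm, with no treatment effect at all. Two forest-plot rows shifted the same way could be read as a consistent effect.

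**Working it through.** The SAP states no sample size, diagnosis rate or power for this subgroup, so there is no figure of its own to reproduce. The mechanism was checked by simulation.

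**Inputs from the SAP:** 1:1 allocation (Background and Aim); SDQ at 4 years compared between arms, adjusted for the baseline measurement (Primary and secondary analyses); strata from status at baseline and 18 months (Subgroup analyses, item a).

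**Assumptions, none in the SAP:** 20% with ASD/ADHD at baseline; 18-month rates varied by arm; a latent trait T correlating 0.8 with diagnostic liability and 0.6 with SDQ at each visit. Age, sex and family clustering were left out.

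**Model**, for 2,000,000 children, with all variables standardised and independent errors e:
- Liability at each visit: L = 0.8·T + 0.6·e. A child is diagnosed at baseline if L exceeds the 80th normal percentile, and at 18 months if L exceeds the threshold giving that arm's rate.
- SDQ at each visit: Y = 0.6·T + 0.8·e. Arm does not enter, so the true effect is zero.
- Within each stratum, Y at 4 years is regressed on arm and baseline Y. The arm coefficient is the bias.

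**Results**, VIA Family minus TAU in SD units, with-diagnosis / without-diagnosis stratum (negative = apparent VIA benefit):

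| Strata defined by | 18-month rate 30% VIA, 20% TAU | 40% VIA, 20% TAU |
|---|---|---|
| 18-month status alone | -0.09 / -0.05 | -0.16 / -0.10 |
| Diagnosis at either visit | -0.05 / -0.04 | -0.11 / -0.08 |
| Both visits versus neither | -0.05 / -0.04 | -0.09 / -0.08 |
| Both visits versus all others | -0.05 / -0.02 | -0.09 / -0.03 |
| Baseline status alone | 0.00 / 0.00 | 0.00 / 0.00 |

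Three further results:
- With equal rates (20% in both arms) every definition gives a difference within 0.003.
- With the rates reversed (20% VIA, 30% or 40% TAU) the sizes are nearly the same and the sign is positive: +0.09 / +0.05 and +0.16 / +0.10 for 18-month status alone.
- Baseline strata stay within 0.005 in every scenario.

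Adjustment for baseline SDQ does not remove the bias, because SDQ measures the trait behind the diagnosis only imperfectly.

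**A second simulation with a different set-up** assumed SDQ SD 6, baseline-to-follow-up correlation 0.6, 15% diagnosed at baseline, 30% of children candidates for a new diagnosis, and strata by either visit. Results for detection among candidates, TAU versus VIA:
- 20% versus 20%: about 0.
- 20% versus 40%: -0.24 / -0.10 points, that is 0.24/6 = 0.04 SD and 0.10/6 = 0.02 SD.
- 20% versus 60%: -0.38 / -0.21 points (0.06 and 0.04 SD).
- 10% versus 50%: -0.49 / -0.18 points (0.08 and 0.03 SD).

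Baseline strata gave 0 to within 0.02 points.

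**Scale.** With SD 6 and correlation 0.6 the residual SD is 6·√(1 − 0.36) = 4.8, and the standard error of an arm difference among n children is 2·4.8/√n. That is 0.68 points for n = 200 and 1.52 for n = 40 (both n assumed, clustering ignored). The largest bias in the second simulation, 0.49 points, is below either.

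**The case against.** The strongest reply is that item a may describe two separate analyses, one by baseline status and one by 18-month status. The sound baseline comparison would then already be planned, and only a supplementary one is at fault. This is a fair reading. It narrows the point without removing it, since the 18-month analysis would still appear among the subgroup results with no caution attached. The SAP also does not say which reading applies, so the classification remains open.

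It can also be said that the bias is modest and rests on assumed, large arm differences in diagnosis. That stands. Nothing in the SAP shows that diagnosis rates differ by arm, and if they do not there is no bias.

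Three stronger readings are tempting, and the SAP supports none of them.

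- *The subgroup will show a false benefit of VIA Family.* The sign follows whichever arm has more 18-month diagnoses. Fewer diagnoses under VIA Family would produce apparent harm.
- *VIA Family raises detection, because its sessions include psychoeducation on emotions or diagnosis.* The per-protocol definition does not say whose diagnosis is meant, and families were eligible because of a parent's illness. The child diagnostic instrument named in Table 1, K-SADS-PL, is listed in Table 2 as a clinician-rated interview. If item a relies on it, status would not depend on a family seeking a diagnosis. Item a does not state its source.
- *Every child who misses the 18-month visit has no stratum and leaves an analysis declared as* "including study participants as randomized regardless of treatment adherence and dropout status". Under an either-visit rule, a child diagnosed at baseline is classified regardless. Table 2 lists only "KSADS, any diagnoses (binary: yes/no") and does not list ASD/ADHD separately at any visit, so a baseline definition would not cure missing status either. The SAP does not say how unknown stratum membership is handled.

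**Conclusion.** The concern holds in limited form. Under every reading of item a, some stratum membership is determined after allocated treatment, and the resulting VIA Family versus TAU contrast within strata is not a randomised comparison. Bias arises only if allocation affects who has ASD/ADHD at 18 months. It is about zero with equal rates and roughly 0.02 to 0.16 SD under assumed rates of 30% or 40% against 20%, with unknown sign. The 0.16 requires both a doubled rate and strata formed from 18-month status alone.

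A reader might infer that the trial's main result is at risk. It is not: the SAP presents these subgroups as exploratory, item a does not enter the primary or secondary hypotheses, and the consequence stops at this subgroup's estimates and forest-plot rows. The change is still worth making, because the flaw is avoidable and the remedy is one line.

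**What to change.** Reword item a so that it compares children with ASD or ADHD at baseline against children with neither at baseline, and delete the reference to the end-of-intervention visit. This brings it into line with items b, c and e and removes the ambiguity between readings. Report ASD/ADHD diagnoses at 18 months by arm as a descriptive result. If a split by 18-month status is kept, show it apart from the baseline subgroup and label it a post-randomisation description without causal interpretation.

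The cost is one line of SAP text. Compared with an either-visit rule, the with-diagnosis stratum becomes somewhat smaller, because children first diagnosed during the intervention count as without.
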